### **11.2 Sample Size Considerations**

With 100 patients, we will have adequate power (i.e.  $\geq 80\%$ ) to detect a 25% difference or greater in admission rates for subjects with low risk lesions with p- value less than 0.05. We assume that the controls will a 100% admission rate. We anticipate 20% or less of all subjects to be diagnosed with a high-risk lesion, we are unlikely to have adequate power to detect a significant difference in the hospital admission rate between the two study groups.

### **11.3 Final Analysis Plan**

The analysis will be conducted in several stages. First, we will compare the baseline characteristics of the two study groups to determine if randomization was successful. We will also compare the baseline characteristics of the study samples by enrollment site. Second, we will compare the VCE and EGD results and classify all study subjects according to whether there is a high versus low risk lesion present. The VCE and EGD results may differ because they are not being performed at the same time and GI bleeds can resolve or change so it is unlikely that there will be perfect agreement between the two modalities. In cases where one modality identifies a low risk lesion and the other one a high-risk lesion, we will classify the lesion as high risk. If the VCE could not adequately visualize the tract, we will classify the results according to the EGD. We will compare the sensitivity and specificity of VCE and EGD for identifying high risk lesions. Finally, we will separately compare the admission rates of high-risk lesions and low risk lesions between the two study groups. We will compare admission rates aggregated across the four study centers as well as within each study center.

For tertiary outcomes, we will compare the outcomes by study group using a chi-square test statistic if the outcome is categorical such as the presence of an adverse event and a t test (normally distributed) or median test (non-normally distributed) if the outcome is continuous such as hospital or ED length of stay.

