**4.4 Study procedure:**

1. Screen potential patients with signs of upper GI bleeding (melena, h/o hematemesis or coffee-ground emesis) from general pool of ED patients. (Form used, *CHEER:1*)
2. Patients who screen as eligible will be approached about potential interest, to review of inclusion and exclusion criteria, and obtain informed consent. (*See below for full list of inclusion/ exclusion criteria.*)
3. Research Coordinator will calculate traditional risk stratification scores (Glasgow – Blatchford and Rockall).
4. All consented patients will be given a study ID and recorded in enrollment log. (Form used, *CHEER:2*)
5. Once enrolled, all subjects will be randomized to either Active Control (AC) [admission plus EGD within hospital stay] or experimental Capsule Endoscopy Risk Assessment (CERA) in ED.
6. Only patients randomized to the experimental arm will receive video capsule endoscopy in the emergency department. 20 to 60 minutes before capsule ingestion, each patient in the experimental arm receives a single dose of intravenous metoclopramide 10 mg (or erythromycin 500mg intravenously if there is a contraindication), which helps to promote gastric motility and improves visualization of the gastric mucosa at endoscopy. The Research Coordinator (RC) will prepare the patient for VCE. (*See below for description of procedure.*)
7. Within 2 hours of presenting to the ED, patient will ingest video capsule-- RC will monitor progress on real-time viewer for passage through pylorus. Upon passing the pylorus, we will record 5 more minutes of video or until battery runs out – whichever occurs first.
8. Patient data will be completed using a standardized data collection tool including the following elements: chief complaint of patient, history of present illness, past medical history, pertinent lab findings, current medications, vital signs, focused physical exam findings and all relevant treatments administered during the ED and hospital stay. (Form Used, *CHEER:3*)

9. At completion of VCE, patient satisfaction regarding VCE will be assessed in patients in the experimental group. (Form used, *CHEER*: 4)
10. For Active Control (AC) group each patient will be admitted.

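### Section 11.3 uses a baseline comparison to judge whether randomisation worked, which it cannot do when allocation is sound, and leaves the GBS out of the length-of-stay comparisons (minor)

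*Combined protocol and SAP*

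**What the plan says.** Section 11.3 opens the analysis with a stated purpose: "we will compare the baseline characteristics of the two study groups to determine if randomization was successful". It adds a second comparison: "We will also compare the baseline characteristics of the study samples by enrollment site". It does not list the characteristics, name a test or significance level, or say what follows if the answer is unfavourable.

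For admission, the plan says "we will separately compare the admission rates of high-risk lesions and low risk lesions between the two study groups", and then "We will compare admission rates aggregated across the four study centers as well as within each study center". It names no test and no baseline covariate. The tertiary outcomes are compared by arm "using a chi-square test statistic if the outcome is categorical", and by "a t test (normally distributed) or median test (non-normally distributed) if the outcome is continuous". No covariate-adjusted analysis appears anywhere in the document.

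Section 4.4, step 3, says "Research Coordinator will calculate traditional risk stratification scores", meaning the GBS and the Rockall score. Randomisation follows at step 5. The GBS decides eligibility (section 5.2 and appendix 18.6, score below 6) and defines the risk scenarios of the cost-effectiveness model (section 3.2, Other Outcomes). It plays no part in the comparison of the arms.

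**The concern.** There are two linked weaknesses.

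First, the baseline comparison is given a job it cannot do. If allocation was carried out properly, any difference between the arms is chance by construction. A large difference then does not show failure, and a small one does not show success. If the comparison is run as a set of significance tests, some items may well fall below 0.05, and the report could carry a wrong statement about randomisation. Because section 11.3 attaches no consequence to the result, whatever is done next would be decided after seeing the data.

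Second, a prognostic score available before randomisation is left out of the tertiary comparisons. Section 2.1 describes the GBS as built to identify bleeds that need admission and urgent intervention, so it may also relate to length of stay. The randomisation text (sections 4.4, 7.1 and 8.2) describes no stratification by GBS or site, so nothing in the stated design or analysis guards against a chance imbalance in the score. Splitting admission by lesion class does not do so, because that class is assigned from VCE and EGD findings after randomisation.

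**Working it through.** **1. The plan's own power figure.** Inputs from section 11.2: 100 subjects, controls 100% admitted, a 25-point difference, p below 0.05, at most 20% high-risk lesions. Assumed: 1:1 allocation and a two-sided test. Low-risk subjects: 100 × 0.80 = 80, or 40 per arm. With mean proportion 0.875, the pooled and unpooled terms are √(2 × 0.875 × 0.125) = 0.4677 and √(0.75 × 0.25) = 0.4330.

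z = (0.25 × √40 − 1.96 × 0.4677) / 0.4330 = 1.53, so power is 93.8%.

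Fisher's exact test gives 95.7%. For 80% power, 27 per arm are needed (34 with continuity correction). The claim of at least 80% is therefore consistent with its inputs, and nothing below alters it.

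**2. Chance of an apparent failure under valid randomisation.** Section 11.3 gives neither a test nor a number of items, so this is conditional on testing k items at 5%. Appendix 18.5 has 13 questions and 12 medical-history boxes, and appendix 18.6 has 8 GBS components. With age, GBS total and Rockall, that makes about 35. For independent items the chance of at least one p below 0.05 is 1 − 0.95^k; the last column is a simulation with tests correlated at 0.3.

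| k | independent | correlated 0.3 |
|---|---|---|
| 5 | 22.6% | not run |
| 10 | 40.1% | 35% |
| 14 | 51.2% | not run |
| 20 | 64.2% | 54% |
| 30 | 78.5% | not run |
| 35 | 83.4% | 71% |

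With Fisher tests on 20 independent binary items of 10% prevalence at 50 per arm, the figure is 30%. A chance signal is more likely than not only from 14 independent items upward.

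**3. Chance imbalance in the GBS.** At 50 per arm, the standard error of a standardised baseline difference is √(2/50) = 0.2 SD. A difference beyond 0.3 SD is 1.5 standard errors, which occurs by chance about 13% of the time.

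**4. Gain on a continuous tertiary outcome.** Linear adjustment for a covariate with correlation r multiplies the residual variance by 1 − r². Take 50 per arm and a standardised difference of 0.5603, which gives 80% power unadjusted. Adjusted power is then Φ(2.80/√(1 − r²) − 1.96). The documents give no r.

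| assumed r | 1 − r² | power |
|---|---|---|
| 0.1 | 0.99 | 80.4% |
| 0.2 | 0.96 | 81.6% |
| 0.3 | 0.91 | 83.6% |
| 0.4 | 0.84 | 86.4% |
| 0.5 | 0.75 | 89.9% |

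**5. Gain on the primary outcome.** This was simulated with 50 per arm, controls all admitted, 30% admission in the experimental arm and GBS uniform on 0–5 (the last two are assumptions). Linear adjustment for GBS and its interaction with arm gave these ratios of adjusted to unadjusted variance: 1.02 if GBS is unrelated to admission, 0.99 at 5 percentage points per GBS unit, and 0.95 at 10 points per unit.

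**The case against.** The strongest reply is that section 11.3 only promises to compare baseline characteristics. An ordinary descriptive table by arm and by site would satisfy it. The chi-square, t and median tests in that section are named for tertiary outcomes, not for baseline. This stands. A reader might infer that a false alarm is likely, but that needs significance tests at 5% on about 14 or more independent items, and the documents state neither. The GBS total, its components, melena and syncope overlap, so independence overstates the risk. What remains is the stated purpose, which a descriptive table cannot serve either.

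It can also be said that soundness of allocation is the very thing being checked, and that subverted allocation could leave a trace at baseline. That is fair, but the trace would be weak evidence and hard to tell from chance with 100 subjects. The allocation procedure and its records answer the question directly.

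A reader might further infer that the plan intends to choose covariates from the imbalances seen. It does not: it provides for no adjustment at all. The risk lies in its silence.

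Nor is the GBS wasted, since it sets eligibility and the cost-model scenarios. It is merely absent from the comparison of arms. Restriction to scores of 0–5 tends to weaken any correlation with stay, and section 2.1 links the score to admission and intervention rather than to length of stay.

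Finally, the variance factor 1 − r² belongs to linear adjustment and is only a guide for rank-based methods. A proportional-odds model could fit hospital stay poorly. If subjects discharged from the ED count as zero days, which the plan does not say, the experimental arm piles up at zero while the control arm, by assumption, does not.

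**Conclusion.** The point holds at minor severity. The sentence on randomisation gives a baseline comparison a purpose it cannot serve under sound allocation. The size of the resulting risk is conditional: 23–40% for 5–10 independent items tested at 5%, and up to 64–79% for 20–30, with lower values under correlation.

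Leaving the GBS out of the length-of-stay comparisons costs some precision and some protection against chance imbalance. The loss of power is negligible at r = 0.1–0.2, modest at r = 0.3, and larger only at r = 0.4–0.5, values that look optimistic on a 0–5 range. All of these correlations are assumptions.

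A reader might infer that the primary admission analysis is weakened as well. The documents do not support this. With controls assumed 100% admitted, GBS can explain no variation in that arm; the simulated variance moves only between about +2% and −5%; and a logistic model would meet separation. The stated power and the primary conclusion are unaffected.

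**What to change.** Replace the sentence in section 11.3 with:

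> Baseline data are summarised by arm and centre without significance tests; the integrity of randomisation is checked from the allocation procedure and log.

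For ED and hospital length of stay, pre-specify a comparison adjusted for GBS and centre, to be used whatever imbalance is seen, with unadjusted results also shown. A linear model on log ED stay would serve, with a rank-based covariate-adjusted analysis of hospital stay in place of the median test. State how subjects discharged from the ED enter the hospital-stay analysis. Adjust binary safety outcomes only if event counts allow. Leave the primary admission comparison unadjusted.

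The cost is analysis-plan wording, since GBS and centre are already recorded. The check of randomisation needs a usable record of allocation. The protocol mentions an enrolment log (section 4.4, step 4) and a randomisation label (section 8.2), so the site files should let the order and timing of consent and assignment be verified.

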During hospital admission, EGD will be performed on all subjects and hemostasis therapy applied as necessary. The study team decided against mandating that EGD be performed within 24 hours of hospital admission. This is a pragmatic trial. The longer the duration between the inpatient EGD and the ED VCE the greater the likelihood of discrepancy in the findings that may be due to a change in the lesion as part of its natural course or due to treatments delivered. However, the primary objective of the study is not to evaluate diagnostic accuracy of the ED VCE. The study team decided it was more important to enroll subjects in a timely manner than exclude subjects because the inpatient EGD was not completed within 24 hours.

For the experimental CERA group, subjects will be monitored for a minimum of 4 hours after ingestion. VCE will be undergo a formal review after completion of the VCE by a staff gastroenterologist with extensive experience in VCEs of the small bowel, colon, and esophagus. Both research personnel and the gastroenterologist will undergo a capsule training program organized by Medtronic and receive accreditation after the training.

11. Subjects in the experimental arm who have no sign of active bleeding, show no serious endoscopic findings on capsule, and have stable hemoglobin, blood pressure and heart rate for at least 4 hours will be discharged from the ED. Discharged CE patients will be scheduled to have an outpatient EGD within 3 days post discharge. Patients will be instructed to return to the ED sooner if signs of new bleeding develops. The Research Coordinator will facilitate setting up this appointment for the patient.

Any subject in the experimental arm with a positive VCE or a negative VCE but has a drop in Hemoglobin  $\geq 3$  at 4 hours or an elevated HR or low BP will be admitted. A hemoglobin drop between 2 and 3 will NOT automatically transfer patient to active control arm. In these cases, decision to proceed will be up to discretion of treating physician. We anticipate that all admitted patients in the experimental arm will undergo EGD in the hospital (same as AC arm.)

12. Primary Outcome: (1) Percent Discharged Home. Assumption is that 100% of Active Control / standard risk assessment will be admitted.
13. Secondary Outcome: Sensitivity and specificity of VCE compared to EGD

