## **11 HYPOTHESIS AND ANALYSIS**

### **11.1 Study Hypotheses**

We hypothesize that there will be no significant difference in the hospital admission rate among subjects diagnosed with a high-risk lesion between the two study groups whereas there will be a significant difference in the hospital admission rate among subjects with a low risk lesion.

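### Section 11.3 builds the high- and low-risk strata from capsule or EGD in the capsule arm but from EGD alone in Active Control, so the stratum admission estimates rest on a different definition in each arm

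*Combined protocol and SAP*

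**What the plan says.** Section 4.4, step 6: "Only patients randomized to the experimental arm will receive video capsule endoscopy in the emergency department". Step 10 admits every Active Control (AC) patient. Step 11 sets the admission rule for CERA: "Any subject in the experimental arm with a positive VCE or a negative VCE but has a drop in Hemoglobin" of at least 3 at 4 hours, or a raised heart rate or low blood pressure, is admitted. Those with no bleeding or serious finding on capsule and stable values are discharged, with an outpatient EGD scheduled within 3 days.

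Section 11.3 then classifies all subjects as high or low risk from the two examinations. Where "one modality identifies a low risk lesion and the other one a high-risk lesion, we will classify the lesion as high risk". The reason given is that "The VCE and EGD results may differ because they are not being performed at the same time and GI bleeds can resolve or change". One exception is stated: "If the VCE could not adequately visualize the tract, we will classify the results according to the EGD". With the strata formed, "we will separately compare the admission rates of high-risk lesions and low risk lesions between the two study groups".

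These strata are not a side analysis. Section 11.1 hypothesises "no significant difference in the hospital admission rate among subjects diagnosed with a high-risk lesion between the two study groups" and a significant difference among low-risk subjects. Section 11.2 claims at least 80% power to "detect a 25% difference or greater in admission rates for subjects with low risk lesions". Section 3.2.1, by contrast, names percent discharged home as the primary outcome, with no strata.

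**The concern.** An AC patient has no capsule result, so the either-modality rule cannot operate in that arm. A CERA patient is high risk if either examination says so, an AC patient only if EGD does. The strata are therefore formed after randomisation, by a different definition in each arm, and in CERA partly from the test that decides admission. Two patients with the same lesion and the same low-risk EGD can land in different strata because one swallowed a capsule.

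At stake are the rates that Section 11 is built on. The low-risk rate is the claimed gain. The high-risk rate shows whether patients with serious lesions were sent home, and any who were are averaged with admitted patients whose capsule was positive and EGD low risk.

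Three things needed to apply the rule are also unstated: which capsule findings count as high risk, which capsule read is used, and how a patient without an EGD is classified. In section 3.2.2, signs of malignancy make a capsule positive but are not on the positive EGD list.

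**Working it through.** **The plan's own figure.** With 20% high risk (section 11.2) and 50 per arm (1:1 allocation is assumed), about 40 per arm are low risk. For 100% v 75% admitted, two-sided 0.05, power is 0.94 by the normal approximation and 0.957 by exact enumeration of Fisher's test. The claim of at least 80% reproduces, so sample size is not the problem.

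**Inputs.** CERA n = 50, of whom 10 are EGD-high and 40 EGD-low. Sensitivity s = 95% and specificity c = 92% (CI 73 to 99%), from the study in section 2.1 that reports high-risk lesions for capsules reaching the duodenum. Assumed, because the documents give no figure: no admissions for haemoglobin, heart rate or blood pressure; u = share of capsules inconclusive, taken as admitted (step 11 does not name their disposition); f = share of capsule-positive, EGD-low patients whose capsule finding counts as high risk.

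**If the read in 11.3 is the one that set disposition.** Let FP = 40(1−u)(1−c), the capsule-positive, EGD-low patients, all admitted.

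- Low-risk admission, 11.3 rule: [40u + FP(1−f)] / (40 − f·FP). EGD-only: (40u + FP) / 40.
- High-risk admission at u = 0, 11.3 rule: (10s + f·FP) / (10 + f·FP). EGD-only: s.

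| Case | FP | CERA low-risk, 11.3 rule | CERA low-risk, EGD-only |
|---|---|---|---|
| c = 92%, u = 0, f = 1 | 3.2 | 0/36.8 = 0% | 3.2/40 = 8.0% |
| c = 92%, u = 0, f = 0.5 | 3.2 | 1.6/38.4 = 4.2% | 8.0% |
| c = 92%, u = 25%, f = 1 | 2.4 | 10/37.6 = 26.6% | 12.4/40 = 31.0% |
| c = 92%, u = 50%, f = 1 | 1.6 | 20/38.4 = 52.1% | 21.6/40 = 54.0% |
| c = 73%, u = 0, f = 1 | 10.8 | 0% | 10.8/40 = 27.0% |
| c = 99%, u = 0, f = 1 | 0.4 | 0% | 0.4/40 = 1.0% |

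At f = 0 there is no gap. High-risk admission (u = 0, f = 1) is (9.5 + 3.2)/13.2 = 96.2% under the rule and 95.0% by EGD alone. AC stays at 100% in both strata under either definition. If inconclusive capsules were instead discharged like negatives (u = 50%, f = 1), the low-risk rates would be 0 v 1.6/40 = 4.0% and the high-risk rates (4.75 + 1.6)/11.6 = 54.7% v 4.75/10 = 47.5%: the same direction.

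**If the offsite read is used.** Section 4.4, step 15 has all capsules re-read offsite, blinded, and the capsule form (18.9) distinguishes real-time from retrospective reads. A patient sent home on a negative site read can then be moved to high risk as a non-admission. Suppose (an assumed count) two discharged EGD-low patients are added to the c = 92%, u = 0, f = 1 case: high-risk admission becomes 12.7/15.2 = 83.6%, below the EGD-only 95.0%. If the offsite read moved only those two, high-risk admission would be 9.5/12 = 79.2% and low-risk admission 3.2/38 = 8.4%, so both shifts would be reversed.

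**Test results.** At 95/92 with u = 0 and f = 1, exact enumeration against 10/10 in AC leaves the high-risk Fisher test non-significant in over 99% of trials under either definition, and the low-risk test is significant in essentially all.

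**The case against.** The case for leaving the rule alone has real parts. AC admission is 100% by design, so reclassifying AC patients alters no AC rate; the distortion is in the CERA rates and in who is being compared. The effect on estimates is modest in plausible cases: 1.2 points in the high-risk stratum at 95/92, and about 2 points in the low-risk stratum if half the capsules are inconclusive and admitted. Section 2.1 puts duodenal visualisation near 50% at 20 to 30 minutes but 98% at 60. Section 11.2 already concedes low power for high-risk lesions. EGD is also not a clean standard: section 4.4 sets no 24-hour limit for inpatient EGD, and a lesion seen on capsule may have resolved by then. That is the plan's own reason for the rule, and it stands as a reason to keep the rule in view. It does not make the rule applicable in AC, where a resolved lesion goes unrecorded.

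On malignancy, the lists in section 3.2.2 define the accuracy endpoint, and both data forms carry a tumour entry. That is a point to clarify, not a demonstrated bias.

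A reader might infer that the rule can only flatter CERA. The documents do not support this, because 11.3 does not name the read. Nor should capsule-positive, EGD-low patients be called false positives: some may be true lesions that resolved. The 64% specificity in section 2.1 would suggest a 36-point gap, but it concerns fresh blood in 25 patients, not high-risk lesions.

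**Conclusion.** The plan is wrong as written on a limited point: the strata behind the 11.1 hypothesis and the 11.2 power statement are defined differently by arm. If the disposition read is used, the rule lowers CERA low-risk admission by 1 to 27 points across the cited specificity interval (f = 1, no inconclusive capsules), by 8.0 points at 92%, and by less with a smaller f or with inconclusive capsules admitted. If the offsite read is used, neither size nor direction is fixed.

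It would go too far to conclude that the trial's main result is biased. Percent discharged home uses no strata and is unaffected, and at these figures the stratum tests are not expected to change; the stratum estimates are what change. All of this rests on 1:1 allocation, 20% EGD-high, accuracy carried over from a cited study, and the assumptions listed above on admissions and inconclusive capsules. It should be fixed before the stratum comparisons are run.

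**What to change.** In section 11.3:

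1. For the between-arm high/low-risk comparison, classify by EGD alone in both arms, from one list of high-risk EGD categories drawn from section 3.2.2, and state whether malignancy is on it. Keep the either-modality rule only as a labelled sensitivity analysis; name the capsule read it uses and the capsule findings that count as high risk.
2. Report the number without an EGD by arm and disposition, and bound the stratum rates by placing them all low, then all high. Discharged CERA patients without an EGD are all non-admissions, so dropping them inflates the CERA rate.
3. State the primary analysis as percent discharged home in all randomised patients by assigned arm, with a confidence interval for the difference that is valid near 100% (for example a Newcombe score interval). Make the strata comparison secondary.

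The change is to wording only; the forms already record EGD findings, date and setting, and EGD after discharge. Exact power for the all-randomised comparison is about 95% (100% v 80% admitted, 50 per arm, Fisher).

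The costs are a less favourable low-risk admission rate, EGD timing that still differs by arm (so lesions resolved before EGD count as low risk), and dependence on discharged patients completing outpatient EGD. Suppose 30% of discharged CERA patients had none (assumed; the documents give no rate). At 95/92 with u = 0, 36.8 EGD-low and 0.5 EGD-high patients are discharged, so 0.3 × 37.3 = 11.19 are missing. Low-risk admission is then 3.2/(3.2 + 25.76 + 11.19) = 8.0% with all placed low and 3.2/(3.2 + 25.76) = 11.0% with all placed high. High-risk admission is 9.5/(9.5 + 0.35) = 96.4% and 9.5/(9.5 + 0.35 + 11.19) = 45.2%. The second range is wide, and its lower end (about 10/21 v 10/10, p = 0.005) would look significant. It must be read as a bound, not an estimate.

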In all ED studies that have been conducted for acute upper gastrointestinal hemorrhage, VCE has performed well when it travels through the pylorus. However, several high-risk lesions were missed if the VCE did not travel through the pylorus before the battery expired. The time to pass the pylorus is variable. At 60 minutes, 98% of capsules visualize the duodenum [6]; when the battery life is only approximately 20-30 minutes, approximately 50% visualize the duodenum (12/25 [7], 44/83 [8], and 7/12 [14]). In one study, the single missed active bleeding occurred in a patient who was bleeding in the post-pyloric duodenum and in whom the VCE battery expired before reaching the post-pyloric region [7]. For standard EGD, the use of pro-kinetic agents such as erythromycin or metoclopramide has improved mucosal visualization and has been increasingly used before the procedure. This strategy, combined with 60 minutes of visualization, will likely increase the accuracy of VCE as well.

The cost of the VCE is an important factor that affects future use in the ED. The physician Medicare national average fee is \$705 for the PillCam UGI and \$50 for the professional fee. Although expensive, VCE may be cost-effective if it safely reduces hospital admissions or emergency EGD. For comparison, in 2011, 236,000 patients received an EGD (International Classification of Diseases, Ninth Revision code 45.13) in the hospital for an upper UGIB, the median length of stay was 4.0 days, and the median charges were \$23,549.17 [12].

A decision-analytic model showed that VCE is cost effective for low- to moderate-risk patients despite increased upfront costs compared with clinical decision rules or nasogastric tubes. The use of VCE in the ED can potentially lead to more patients being safely discharged from the ED. The hospital admission is the single most expensive decision made by an emergency physician. Chandran et al [8] showed that the higher sensitivity of VCE compared with the Glasgow-Blatchford Score would have saved \$1691 per VCE by increasing the number of patients who could receive an outpatient EGD.

Currently, the VCE does not replace the need for traditional EGD when hemostasis or biopsy is needed. Technological advancements may allow a VCE operator to control movement of the capsule, collect biopsy samples, and perform therapeutic functions.

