#### 3.2 Study Outcome Measures

3.2.1 Primary Outcome: (1) Percent Discharged Home. Assumption is that 100% of Active Control (AC) group will be admitted.

3.2.2 Secondary Outcome: Sensitivity and specificity of VCE compared to EGD. *Endpoints will be defined in the following way:*

Positive Video Capsule Endoscopy will be defined as:

1. Fresh blood or evidence of active bleeding visualized in upper GI tract.
2. Coffee ground blood visualized in upper GI tract, but no active bleeding seen.
3. A High Grade Non-Variceal Lesion (Forrest Ia, Ib, IIa or IIb).
4. Signs of Variceal Hemorrhage.
5. Signs of malignancy visualized in upper GI tract.

Negative VCE:

5. Clean stomach and duodenum, no fresh blood or coffee ground.
6. Upper GI pathology non-causative/ incidental.
7. A low grade non-Variceal lesion (Forrest IIc, III).

An Inconclusive VCE:

8. Any capsule that does not pass the pylorus before battery life is expired (and does not detect lesion in stomach or esophagus).

Positive EGD

1. Fresh blood or evidence of active bleeding.
2. Coffee ground but no active bleeding seen.
3. A High Grade Non-Variceal Lesion (Forrest Ia, Ib, IIa or IIb).
4. Signs of Variceal Hemorrhage.

Negative EGD

5. Clean stomach and duodenum, no fresh blood or coffee ground.
6. Upper GI pathology non-causative/ incidental.
7. A low grade non-variceal lesion (Forrest IIc, III).

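### Section 11.3 does not say how an inconclusive capsule enters VCE sensitivity and specificity; if its EGD-classification rule is carried into that table, failed capsules count as agreement

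*Combined protocol and SAP*

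**What the plan says.** Section 3.2 sets the secondary outcome as "Sensitivity and specificity of VCE compared to EGD". It sorts capsule results into positive, negative and inconclusive, the last being "Any capsule that does not pass the pylorus before battery life is expired (and does not detect lesion in stomach or esophagus". EGD results have two classes only.

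The second stage of section 11.3 is to compare the VCE and EGD results and "classify all study subjects according to whether there is a high versus low risk lesion present". Two rules follow. For disagreement: "In cases where one modality identifies a low risk lesion and the other one a high-risk lesion, we will classify the lesion as high risk". For a capsule that saw too little: "If the VCE could not adequately visualize the tract, we will classify the results according to the EGD". The next sentence turns to accuracy: "We will compare the sensitivity and specificity of VCE and EGD for identifying high risk lesions". It names no reference standard and gives no rule for the inconclusive class. The section then compares admission rates separately for high-risk and low-risk lesions.

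The background (section 2.1) warns that "several high-risk lesions were missed if the VCE did not travel through the pylorus before the battery expired".

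**The concern.** Sensitivity and specificity need a two-way decision for every capsule in the table, and section 3.2 creates a third outcome. Section 11.3 leaves the analyst to choose among filling in the EGD answer, dropping the capsule, counting it as positive, counting it as negative, or keeping it as a separate row. The one sentence that mentions failed capsules points to the first of these, which completes the index test from its own reference.

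Failure to pass the pylorus is the capsule's best-documented weakness in section 2.1, so the choice matters for how the secondary outcome is read. It matters more because numbers are small. With about 50 subjects in the capsule (CERA) arm (1:1 allocation is an assumption; the ratio is not stated) and the 20% or fewer high-risk lesions anticipated in section 11.2, about 10 subjects would be EGD-positive. One inconclusive capsule among them is worth 1/10, or 10 percentage points of sensitivity, depending on whether it is counted as a detection or a non-detection.

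**Working it through.** **The plan's own figures.** Section 11.2 claims at least 80% power for a 25-point difference in admission among low-risk subjects, against 100% in controls. With 40 low-risk subjects per arm (80% of 50, 1:1 assumed) and two-sided 0.05, pooled-z power is 93.8% and Fisher exact power 95.7%, so the claim holds as a lower bound. This point does not touch it. No target or sample size is given for accuracy.

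Section 2.1 says about half of capsules visualise the duodenum on a 20–30 minute battery. Pooling its three studies gives (12 + 44 + 7)/(25 + 83 + 12) = 63/120 = 52.5%. It gives 98% at 60 minutes.

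**Inputs.**
- p, the share of capsules that are conclusive: 52.5% and 98% from section 2.1, and 80% as an assumed middle value.
- s = 95% and c = 92%, the sensitivity and specificity that section 2.1 reports for capsules that reached the duodenum. That they carry over to this trial is an assumption.
- In the table, inconclusive status is taken as unrelated to EGD status.

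**Formulas (sensitivity; specificity).**
- Filled from EGD: p·s + (1 − p); p·c + (1 − p)
- Dropped: s; c
- Counted negative: p·s; p·c + (1 − p)
- Counted positive: p·s + (1 − p); p·c
- Kept in both denominators as neither positive nor negative: p·s; p·c

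Example at p = 0.525, filled from EGD: 0.525 × 0.95 + 0.475 = 97.4%, and 0.525 × 0.92 + 0.475 = 95.8%. Kept in both denominators: 0.525 × 0.95 = 49.9%, and 0.525 × 0.92 = 48.3%.

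| Handling of inconclusive VCE | p = 98% | p = 80% | p = 52.5% |
|---|---|---|---|
| Filled from EGD | 95.1 / 92.2 | 96.0 / 93.6 | 97.4 / 95.8 |
| Dropped | 95.0 / 92.0 | 95.0 / 92.0 | 95.0 / 92.0 |
| Counted negative | 93.1 / 92.2 | 76.0 / 93.6 | 49.9 / 95.8 |
| Counted positive | 95.1 / 90.2 | 96.0 / 73.6 | 97.4 / 48.3 |
| Kept in both denominators | 93.1 / 90.2 | 76.0 / 73.6 | 49.9 / 48.3 |

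**Reading the table.** Filling from EGD exceeds conclusive-capsule accuracy by 0.1/0.2 points at 98% and 2.4/3.8 points at 52.5%. The direction does not need the independence assumption: adding only correct results to a proportion below 100% raises it, whatever the inconclusive share in each EGD class.

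**The disagreement rule.** If the either-test-high class were used as the reference, every subject with a high-risk VCE would be classed high. No VCE false positive could exist, and VCE specificity would be 100% by construction. The reference therefore has to be stated as well.

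**The case against.** The strongest defence is that the rule was never meant for the accuracy table. It stands in the step that assigns each subject a lesion class, beside the disagreement rule, and the admission comparison needs that class. If these rules rewrote test results, the disagreement rule would remove every VCE–EGD difference before accuracy was computed, yet the same paragraph expects the modalities to differ. This is the more natural reading. A reader might infer that the plan plainly fills in failed capsules from EGD and so overstates accuracy; the documents do not support that. Still, section 11.3 uses *results* elsewhere for the readings of the two modalities, and it offers no other rule for failed capsules, so the ambiguity is real.

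Three further inferences also go too far.
- That both measures are overstated whatever is done. Against counting inconclusive as negative, EGD-filling leaves specificity unchanged; against counting it as positive, sensitivity is unchanged. Dropping leaves conclusive-capsule accuracy as it is and misleads only if reported as accuracy in everyone given a capsule, which the plan does not say it will do.
- That the plan hides the failure. Section 3.2 defines it, and the PillCam data form (section 18.9, item j) records pyloric passage before battery expiry.
- That accuracy is really about 50%. The 50%/48% pair needs the low passage rate and a failure counted in both EGD classes; no single binary coding gives both. Under section 3.2 a non-passing capsule that shows an esophageal or gastric lesion is conclusive, so the passage rate is a floor for p. Section 4.4 also gives experimental-arm patients a motility agent before ingestion. Section 2.1 describes both 30 minutes of imaging and an expectation of 60, so the rate in this trial is uncertain.

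One limit applies to the defence of dropping. Because of that same definition, non-passing capsules stay in the table only when they show a lesion. Lesions beyond the pylorus that went unseen leave the sensitivity denominator, so conclusive-only sensitivity may flatter the capsule, while specificity need not.

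Finally, section 4.4 says diagnostic accuracy is not the primary objective. That stands and limits the weight of the point.

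**Conclusion.** The concern holds as a gap in the plan with a possible bias, not as a demonstrated overstatement. The analysis of the secondary outcome cannot be reproduced from section 11.3, and the only stated rule, if carried into the accuracy table, turns failed capsules into automatic agreement. The resulting excess over conclusive-capsule accuracy is negligible at 98% conclusive and a few points at the low extreme. The larger issue is what the figure describes: the gap between conclusive-only and all-capsule accuracy is about 2 points on each measure at 98% conclusive, 18–19 points at 80%, and 44–45 points at 52.5%. These sizes rest on 95%/92% in conclusive capsules, on the assumed p, and on independence from lesion status. Percent discharged home and the stated power are untouched, so this should be settled before analysis but does not threaten the trial's main result.

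**What to change.** Add one paragraph to section 11.3, to this effect:

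- The EGD rule for non-visualising capsules and the either-test-high rule set only the subject-level lesion class used in the admission comparison. Neither changes a VCE result.
- Accuracy is assessed among CERA subjects who have an EGD, with EGD alone as the reference.
- An inconclusive VCE stays inconclusive. Results are shown as a 3 × 2 table (VCE positive, negative, inconclusive by EGD positive, negative).
- All-capsule sensitivity is VCE-positive over all EGD-positive, and all-capsule specificity is VCE-negative over all EGD-negative. Inconclusive, unswallowed and unreadable capsules are kept in both denominators.
- Conclusive-only sensitivity and specificity, labelled as such, and the percent conclusive are reported beside them.

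Which pair is given first is a matter of preference; both should be fixed in advance. The cost is a paragraph of wording and less favourable all-capsule figures. Pyloric passage is already recorded on the PillCam form. No change to sample size or to the primary analysis is needed.
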